**Table 3 Study plan detailing the procedures during the Treatment Period Year 2 through Year 3 or End of Study**

Visit Month (Year 2)	V15	V16	V17	V18	V19	V20 (M18)	V21	V22	V23	V24	V25	V26	V27 (M24)
Study Week (Year 2)	W56	W60	W64	W68	W72	W76	W80	W84	W88	W92	W96	W100	W104
Visit Month (Year 3)	V28	V29	V30	V31	V32	V33 (M30)	V34	V35	V36	V37	V38	V39	V40 (M36)
Study Week (Year 3)	W108	W112	W116	W120	W124	W128	W132	W136	W140	W144	W148	W152	W156 (EDV) a
Procedure/Visit Window	±7 D	±7 D	±7 D	±7 D	±7 D	±7 D	±7 D	±7 D	±7 D	±7 D	±7 D	±7 D	±7 D
Physical examination, weight													X o
Vital signs	X	X	X	X	X	X	X	X	X	X	X	X	X o
ECG													X
Pap smear b													X
Laboratory													
Blood test for TB c,d,e (QFT-G In-Tube Test)			X e			X e							X
Serum chemistry, haematology, and urinalysis f						X							X o
Urine pregnancy test g	X	X	X	X	X	X	X	X	X	X	X	X	X
Hepatitis B virus DNA h			X			X			X				X

**Table 3 Study plan detailing the procedures during the Treatment Period Year 2 through Year 3 or End of Study**

Visit Month (Year 2)	V15	V16	V17	V18	V19	V20 (M18)	V21	V22	V23	V24	V25	V26	V27 (M24)
Study Week (Year 2)	W56	W60	W64	W68	W72	W76	W80	W84	W88	W92	W96	W100	W104
Visit Month (Year 3)	V28	V29	V30	V31	V32	V33 (M30)	V34	V35	V36	V37	V38	V39	V40 (M36)
Study Week (Year 3)	W108	W112	W116	W120	W124	W128	W132	W136	W140	W144	W148	W152	W156 (EDV) a
Procedure/Visit Window	±7 D	±7 D	±7 D	±7 D	±7 D	±7 D	±7 D	±7 D	±7 D	±7 D	±7 D	±7 D	±7 D

**Table 3 Study plan detailing the procedures during the Treatment Period Year 2 through Year 3 or End of Study**

Visit Month (Year 2)	V15	V16	V17	V18	V19	V20 (M18)	V21	V22	V23	V24	V25	V26	V27 (M24)
Study Week (Year 2)	W56	W60	W64	W68	W72	W76	W80	W84	W88	W92	W96	W100	W104
Visit Month (Year 3)	V28	V29	V30	V31	V32	V33 (M30)	V34	V35	V36	V37	V38	V39	V40 (M36)
Study Week (Year 3)	W108	W112	W116	W120	W124	W128	W132	W136	W140	W144	W148	W152	W156 (EDV) a
Procedure/Visit Window	±7 D	±7 D	±7 D	±7 D	±7 D	±7 D	±7 D	±7 D	±7 D	±7 D	±7 D	±7 D	±7 D
Safety													
Assessment of AEs, AESIs, SAEs	X	X	X	X	X	X	X	X	X	X	X	X	X o
Modified Flare Index						X							X
Concomitant medications, including SLE medications	X	X	X	X	X	X	X	X	X	X	X	X	X o
Tacrolimus trough levels m	X	X	X	X	X	X	X	X	X	X	X	X	X

**Table 3 Study plan detailing the procedures during the Treatment Period Year 2 through Year 3 or End of Study**

Visit Month (Year 2)	V15	V16	V17	V18	V19	V20 (M18)	V21	V22	V23	V24	V25	V26	V27 (M24)
Study Week (Year 2)	W56	W60	W64	W68	W72	W76	W80	W84	W88	W92	W96	W100	W104
Visit Month (Year 3)	V28	V29	V30	V31	V32	V33 (M30)	V34	V35	V36	V37	V38	V39	V40 (M36)
Study Week (Year 3)	W108	W112	W116	W120	W124	W128	W132	W136	W140	W144	W148	W152	W156 (EDV) a
Procedure/Visit Window	±7 D	±7 D	±7 D	±7 D	±7 D	±7 D	±7 D	±7 D	±7 D	±7 D	±7 D	±7 D	±7 D
Investigational product													
Investigational product administration n	X	X	X	X	X	X	X	X	X	X	X	X	X p

AE = adverse event; AESI = adverse event of special interest; AIS = adenocarcinoma in situ;

CIN = cervical intraepithelial neoplasia; CIS = carcinoma in situ;

D = day; DMARD = disease-modifying antirheumatic drug; dsDNA = double-stranded deoxyribonucleic acid; ECG = electrocardiogram; EDV = Early Discontinuation Visit;

LLOQ = lower limit of quantitation; M = month;

QFT-G = QuantiFERON®-TB

Gold; SAE = serious adverse event;

LE = systemic lupus erythematosus;

SOC = standard of care; TB = tuberculosis; V = Visit; W = week;

a Subjects who prematurely discontinue investigational product will have the Early Discontinuation Visit within 4 weeks after the last dose of investigational product.

b Females with intact cervix must have a Pap smear completed and without documented malignancy (eg. no signs of CIN grade III, CIS, or AIS) within 90 days before Day 1 or up until 30 days after randomization, ie, before dosing at V2. Pap smears should thereafter be performed yearly and all female subjects with an intact cervix should have a Pap smear performed within 3 months of the last IP dose, eg, at the end of study or at the early discontinuation visit. If the Pap smear is abnormal, but without malignancy, it should be repeated as per the subject's gynaecologist's recommendation. If the subject's gynaecologist has recommended a repeat Pap smear be performed at a specified interval, the Pap smear should be obtained as recommended and the report provided in the source document. Since access to a Pap smear may vary by country, the Sponsor recommends that local guidelines are used for obtaining routine follow-up Pap smears in females who have received immunomodulators or immunosuppressive treatment.

c Interferon-gamma release assay (IGRA) using QFT-G In-Tube Test.

d If a subject has a newly positive QFT-G test at any time during the study or at Week 156, the subject will undergo a chest x-ray to rule out the presence of active TB or other clinically relevant findings. Posterior-anterior and lateral images are required.

- e If subject has a newly indeterminate QFT-G test, it must be repeated every 3 months for the first year and every 6 months thereafter unless it reverts to negative.
- f Investigators should apply local practices for safety monitoring, eg, by serum chemistry tests, in case SOC dose is changed, eg, increased, and/or new DMARD is added.
- g Urine pregnancy test in females of childbearing potential.
- h Only subjects with Hepatitis B core antibody positivity at enrolment of Studies D3461C00004 or D3461C00005. To remain eligible in the LTE study, subject Hepatitis B virus DNA levels must remain below the LLOQ as per the central laboratory.
- i [REDACTED]
- j [REDACTED]
- k [REDACTED]
- l [REDACTED]
- m Monthly tacrolimus trough levels in subjects receiving tacrolimus as standard of care SLE therapy. These subjects must maintain tacrolimus trough levels below the central laboratory upper limit of the therapeutic range based on monthly measurements.
- n Investigational product will be administered as an IV infusion via an infusion pump over a minimum of 30 minutes.
- o If the subject is unwilling to continue with any study visits, including EDV, or is willing to continue with only selected study assessments, at a minimum, these assessments should be completed.
- p No investigational product dosing occurs at Week 156 or EDV.

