- (d) **Newly indeterminate** (as confirmed on retest unless prior positive QFT-G was documented, along with completed treatment for latent TB) or **indeterminate but not newly indeterminate** QFT-G test result at Week 52 of Studies D3461C00004 or D3461C00005 from the study central laboratory with ongoing QFT-G testing for TB according to the Study Plan

The QFT-G test results obtained at Week 52 of Studies D3461C00004 or D3461C00005 should be available within 30 days of randomisation, but prior to the second dose of investigational product administration (Visit 2/Week 4). The PRA Medical Monitor may be contacted for questions.

9. In the opinion of the Investigator, subject must be able to comprehend the ICF and all protocol-related assessments, and be able to complete all study-required documents, procedures, and outcome measures

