## **4. STUDY PLAN AND TIMING OF PROCEDURES**

**Table 2 Study plan detailing the procedures during the Treatment Period Year 1**

Visit Month	Day 1 V1 a	V2	V3	V4	V5	V6	V7 (M6)	V8	V9	V10	V11	V12	V13	V14 (M12)
Study Week (Year 1)	W0	W4	W8	W12	W16	W20	W24	W28	W32	W36	W40	W44	W48	W52
Procedure/Visit Window		±7 D	±7 D	±7 D	±7 D	±7 D	±7 D	±7 D	±7 D	±7 D	±7 D	±7 D	±7 D	±7 D
Written informed consent	X													
Physical examination, weight and height b	X													X
Vital signs	X	X	X	X	X	X	X	X	X	X	X	X	X	X
ECG	X													X
Pap smear c	X													X
Laboratory														
Blood test for TB d,e,f (QFT-G In-Tube Test)	X			X f			X f							X
Serum chemistry, haematology, and urinalysis g	X	X	X	X			X			X				X
Urine pregnancy test h	X	X	X	X	X	X	X	X	X	X	X	X	X	X
Hepatitis B virus DNA i	X			X			X			X				X
HIV test j	X													

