- c Females with intact cervix must have a Pap smear completed and without documented malignancy (eg. no signs of CIN grade III, CIS, or AIS) within 90 days before Day 1 or up until 30 days after randomization, ie, before dosing at V2. Pap smears should thereafter be performed yearly and all female subjects with an intact cervix should have a Pap smear performed within 3 months of the last IP dose, eg, at the end of study or at the early discontinuation visit. If the Pap smear is abnormal, but without malignancy, it should be repeated as per the subject's gynaecologist's recommendation. If the subject's gynaecologist has recommended a repeat Pap smear be performed at a specified interval, the Pap smear should be obtained as recommended and the report provided in the source document. Since access to a Pap smear may vary by country, the Sponsor recommends that local guidelines are used for obtaining routine follow-up Pap smears in females who have received immunomodulators or immunosuppressive treatment.
- d Interferon-gamma release assay (IGRA) using QFT-G In-Tube Test.
- e If subject has a newly positive QFT-G test at Day 1/Visit 1 or at any time during the study, the subject will undergo a chest x-ray. Posterior-anterior and lateral images are required.
- f If subject has a newly indeterminate QFT-G test, it must be repeated every 3 months for the first 6 months, and every 6 months thereafter unless it reverts to negative.
- g Investigators should apply local practices for safety monitoring, eg, by serum chemistry tests, in case SOC dose is changed, eg, increased, and/or new DMARD is added.
- h Urine pregnancy test in females of childbearing potential.
- i Only subjects with Hepatitis B core antibody positivity at enrolment of Studies D3461C00004 or D3461C00005. To remain eligible in the LTE study, subject Hepatitis B virus DNA levels must remain below the LLOQ as per the central laboratory.
- j HIV test only in subjects not tested in Studies D3461C00004 or D3461C00005.
- k [REDACTED]
- l [REDACTED]
- m [REDACTED]
- n [REDACTED]
- o Monthly tacrolimus trough levels in subjects receiving tacrolimus as standard of care SLE therapy. These subjects must maintain tacrolimus trough levels below the central laboratory upper limit of the therapeutic range based on monthly measurements.
- p Investigational product will be administered as an IV infusion via an infusion pump over a minimum of 30 minutes.

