#### 5.2.7.1 Tuberculosis results at time of randomisation/Week 52 of the Phase 3 Study D3461C00004 or D3461C00005

- If the QFT-G test result was **negative** and there is no known history of recent exposure to individuals with active TB, the subject may be randomised.
- If the QFT-G test result was **newly positive**, a chest x-ray must be performed. If the chest x-ray shows no evidence of active TB, and the subject has no symptoms or medical history consistent with active TB, the subject must have a retest. If the retest is positive, the subject must start on prophylaxis within 30 days of randomisation, but prior to the second dose (Visit 2/Week 4) in the LTE study. The subject should be referred to a TB specialist. If a TB specialist is not available, the local country guidelines should be followed for further diagnostic work up and anti-TB treatment regimens. If no local guidelines exist for immunocompromised

individuals, then USA guidelines may be followed. This should be reported as an AESI. The QFT-G test must be repeated annually.

- If the QFT-G test was **positive but not newly positive**, the subject must have been diagnosed with latent TB and must have documentation confirming completion of appropriate OR initiate treatment for latent TB within 30 days of randomisation, but prior to the second dose (Visit 2/Week 4).
- If the QFT-G test result was newly indeterminate (as confirmed on retest unless prior positive QFT-G was documented, along with completed treatment for latent TB) or indeterminate but not newly indeterminate, further QFT-G testing will be done according to the Study Plan ([Table 2](#) and [Table 3](#)).

QFT-G testing is performed at least annually and in some cases more often, depending on the result. Refer to the Study Plan ([Table 2](#) and [Table 3](#)).

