#### 5.2.7.2 Tuberculosis monitoring during the study

At every visit, sites should ensure that the subject has no signs or symptoms of active TB, no recent contact with anyone with active TB, and there is no history of latent (unless diagnosed with documentation of initiation of appropriate treatment) or active TB.

If during the trial a subject is determined to have a:

- **Negative** QFT-G test result, only the annual TB testing is required.
- **Newly positive** QFT-G test result, a chest x-ray has to be performed, and the subject should be referred to a TB specialist. If a TB specialist is not available, the local country guidelines should be followed for further diagnostic work up and anti-TB treatment regimens. If no local guidelines exist for immunocompromised individuals, then USA guidelines may be followed. This should be reported as an AESI. The QFT-G test must be repeated annually.
- For **indeterminate** QFT-G test result, refer to Section [5.2.7.1](#).

QFT-G testing is performed at least annually and in some cases more often, depending on the result. Refer to the Study Plan ([Table 2](#) and [Table 3](#)).

#### 5.2.7.3 Tuberculosis monitoring at Week 156

- **Negative** QFT-G test result: No further testing is required.
- **Newly positive** QFT-G test result at Week 156 or later: Follow prior recommendations for newly positive QFT-G result during study.

- **Newly indeterminate** QTF-G test result (as confirmed on retest unless prior positive QTF-G was documented, along with completed treatment for latent TB): Repeat at Follow-up Visit 1 (8 weeks post-final dose).
  - If negative, no further testing
  - If indeterminate, repeat again at Follow-up Visit 2 (12 weeks post-final dose).

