**Randomisation**

[REDACTED]

HbA1c in diabetic subjects only

HBV DNA (testing every 3 months for subjects with HBcAb positivity at enrolment of Studies D3461C00004 or D3461C00005. To remain eligible in the LTE study, subject HBV DNA levels must remain below the LLOQ as per the central laboratory.)

HIV test (only in subjects not tested in Studies D3461C00004 or D3461C00005)

CK

[REDACTED]

Urine protein/creatinine ratio

QFT-G

---

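### Table 3's rule for repeating a newly indeterminate TB test contradicts both its own grid and the rule in Table 2, by one month-9 test per result

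*Protocol*

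**What the plan says.** The repeat rule for a newly indeterminate QFT-G result appears only in footnotes to the two study-plan tables.

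- Protocol Table 2 (Year 1), footnote f: "it must be repeated every 3 months for the first 6 months, and every 6 months thereafter unless it reverts to negative".
- Protocol Table 3 (Years 2 and 3), footnote e: "it must be repeated every 3 months for the first year and every 6 months thereafter unless it reverts to negative".

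The body text gives no interval for results before Week 156. Inclusion criterion 8(d) in Section 3.1 admits indeterminate results "with ongoing QFT-G testing for TB according to the Study Plan". Section 5.2.7.1 says "further QFT-G testing will be done according to the Study Plan". Section 5.2.7.2 sends indeterminate results back to 5.2.7.1 and adds that "QFT-G testing is performed at least annually and in some cases more often, depending on the result", again referring to the tables. Section 5.2.7.3 has its own rule for a newly indeterminate result at Week 156: repeat at Follow-up Visit 1 and, if still indeterminate, at Follow-up Visit 2.

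**The concern.** The footnotes share the same trigger and the same exit and are both mandatory, but they differ on how long quarterly testing lasts. The TB row of Table 3 does not show the extra test that its own footnote requires. Since the body text refers sites back to the tables, nothing outside them settles the matter.

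At stake is how often a subject with an unreadable TB status is retested while four-weekly dosing continues. Section 5.2.7.2 makes a newly positive test a reportable AESI, and Section 6.5 lists latent TB among the AESIs whose rates are the primary outcome (Section 2.1). Section 6.5.5 withholds investigational product after latent TB is confirmed until its treatment has begun, so the date of detection also bears on dosing. A site that follows the footnote and a site that follows the grid would look for the same event at different frequencies, and the second would be in deviation from footnote e.

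**Working it through.** No stated figure needs reproducing. The check expands each footnote into visit weeks and compares them with the marks in the grids.

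**Inputs**

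1. TB row, Table 2: Weeks 0, 12, 24 and 52. The marks at Weeks 12 and 24 carry superscript f.
2. TB row, Table 3: Weeks 64/116, 76/128 and 104/156. The first two pairs carry superscript e.
3. The protocol's visit pattern for quarterly testing. Table 5 describes "HBV DNA (testing every 3 months for subjects with HBcAb positivity at enrolment of Studies D3461C00004 or D3461C00005", and the HBV DNA rows of Tables 2 and 3 are marked at Weeks 0, 12, 24, 36, 52; 64, 76, 88, 104; and 116, 128, 140, 156. In this protocol, then, month 9 of a year falls on Week 36, 88 or 140.
4. Footnote f in months after the result: 3, 6, 12, 18 and so on. Footnote e: 3, 6, 9, 12, 18 and so on.

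**Assumption.** Neither footnote says from when its period is counted. I count from the first indeterminate result. The conditional marks at Weeks 64 and 116 fit this: each lies 12 weeks after an annual test (52 + 12 and 104 + 12).

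**Expansion for a result that stays indeterminate**

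| First indeterminate | Footnote f | Footnote e | Required but unmarked |
|---|---|---|---|
| Week 52 | 64, 76, 104, 128, 156 (5 tests) | 64, 76, 88, 104, 128, 156 (6 tests) | Week 88, under e |
| Week 104 | 116, 128, 156 (3 tests) | 116, 128, 140, 156 (4 tests) | Week 140, under e |

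Every test under footnote f has a mark in the grid. Footnote e requires one more test, at month 9, which has none.

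**Intervals in the first year after the result**

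- Week 52 result, footnote f and the grid: 64 − 52 = 12, 76 − 64 = 12, 104 − 76 = 28 weeks.
- Week 52 result, footnote e: 12, 12, 88 − 76 = 12, 104 − 88 = 16 weeks.
- The Week 104 result gives the same intervals: 12, 12, 28 against 12, 12, 12, 16.

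The longest interval is therefore 28 weeks against 16. A 28-week interval holds 28/4 = 7 scheduled infusions (Weeks 76 to 100, or 128 to 152). A conversion that a month-9 test would have shown is seen 104 − 88 = 16 weeks later at the annual test (likewise 156 − 140 = 16).

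**Result first indeterminate at Day 1.** Table 2 governs Year 1, and its footnote and grid agree: Weeks 12, 24 and 52. From Year 2 both footnotes give 6-monthly tests, at Weeks 76, 104, 128 and 156. There is no conflict unless a Years 2 and 3 footnote is applied backwards to Year 1.

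**The case against.** The best defence is that the tables are sequential. Table 2 governs Year 1 and Table 3 governs Years 2 and 3, so sites do not choose between them and the rule may legitimately change over time. That disposes of any conflict in Year 1. It does not help Table 3, whose footnote and grid disagree within the same table. Nor does it settle a Week 52 result, which is recorded under Table 2 but repeated under Table 3.

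A second defence is that other TB safeguards continue. Section 5.2.7 requires annual QFT-G testing for everyone. Section 5.2.7.2 requires a check for signs, symptoms and recent contact at every visit, and Section 7.2.2 requires confirmation of a TB evaluation before each infusion. This stands and limits the consequence.

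A reader might infer several stronger things that the documents do not support:

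- **That the needed visits are missing.** The visits at Weeks 36, 88 and 140 all exist; at issue in Table 3 is the TB-test mark at Weeks 88 and 140.
- **That three 28-week gaps are in dispute for one subject** (Weeks 24 to 52, 76 to 104, 128 to 156). Footnote e itself becomes 6-monthly after a year, so at most one interval differs for any one result.
- **That seven infusions pass without TB surveillance.** They pass without a scheduled blood test; the visit checks continue.
- **That every indeterminate result is affected.** Both footnotes are limited to newly indeterminate results, and Section 5.2.7.3 covers Week 156 separately.

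**Conclusion.** The contradiction is real and lies in an operative monitoring rule. Table 3 footnote e conflicts with Table 3's TB row and with Table 2 footnote f, for results first indeterminate at LTE Week 52 and for those arising in Years 2 and 3 before Week 156. Its size is one month-9 test per result, with a longest first-year interval of 28 weeks by the grid against 16 by the footnote.

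It is tempting to read this as a bias in the primary outcome. The documents do not support that: the rule is the same for all treatment groups, the Investigator and site staff stay blinded, and the annual test occurs under either reading. What is shown is a possible difference between sites in how often latent TB is looked for, and an avoidable protocol deviation for any site that follows the grid. The number of subjects affected is not given, so no effect on AESI rates can be calculated.

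The finding rests on two things: reading the table rows by column position, which the matching column counts (14 and 13) and the quarterly HBV DNA row support, and counting the repeat period from the first indeterminate result. It should be corrected, but it does not threaten the study's conclusions.

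**What to change.** Reconcile Table 2 footnote f, Table 3 footnote e and the TB rows of both tables so that they state one consistent repeat schedule and one starting point for counting it. Refer to that schedule in Section 5.2.7.2. The sponsor's medical team decides the interval and how it is counted; this review takes no position on either.

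The cost is wording and table marks in the next protocol version. If the reconciled schedule keeps a month-9 test, it adds at most one blood sample per newly indeterminate result relative to the current grid, at a visit that already exists. If it does not, there is no added sampling.

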**Table 4 Study plan detailing the procedures during Follow-up**

Visit	Follow-up Visit 1 a	Follow-up Visit 2 a
Study Week	8 weeks post-final dose	12 weeks post-final dose
Procedure/Visit Window	±3 D	±3 D
[REDACTED]		
Physical examination, weight		X
Vital signs	X	X
Serum chemistry, haematology, and urinalysis	X	X
Urine pregnancy test in females of childbearing potential	X	X
[REDACTED]		
Assessment of AEs, AESIs, SAEs	X	X
Concomitant medications	X	X

AE = adverse event; AESI = adverse event of special interest; [REDACTED]

[REDACTED] D = day; dsDNA = double-stranded deoxyribonucleic acid; [REDACTED]

[REDACTED] AE = serious adverse event; [REDACTED]

a Follow-up assessments are to be completed when subjects complete the study (eg, early termination or after the treatment period).

## **4.1 Randomisation**

Before randomisation (Day 1/Visit 1/Week 0), subjects will be assessed to ensure that they have signed the ICF and meet eligibility criteria. Once the subject is randomised, relevant data must be captured in the appropriate LTE system. Events that occur prior to randomisation in the LTE study should be reported in Studies D3461C00004 or D3461C00005. Subjects who do not sign the ICF and/or who do not meet the eligibility criteria must not be randomised into the LTE study.

The Week 52 assessments of the Phase 3 Studies D3461C00004 or D3461C00005 will serve as Day 1/Visit 1/Week 0 assessments of the LTE study; additional procedures that are part of the LTE study will also be performed. If Day 1/Visit 1/Week 0 occurs more than 30 days after the Week 52 final visit of the Phase 3 Studies D3461C00004 or D3461C00005, the PRA Medical Monitor must be contacted. In case the Day 1/Visit 1/Week 0 occurs >60 days after the Week 52 final visit of the pivotal studies, additional safety laboratory tests, eg, haematology, liver function tests, and serum creatinine, might be required as judged by the PRA/AZ medical monitor. The rationale for delayed start, date of last dose of study drug, and subject compliance in the prior study will be reviewed. In addition, all procedures for Day 1/Visit 1/Week 0 must be completed.

